Mozambique has one of the world's highest HIV/AIDS burdens, and is the home of one of the world's poorest and most medically underserved regions, Zambézia province, located in north-central Mozambique (Fig.1). Adult HIV prevalence in 2009 was 12.6%, but among pregnant women was substantially higher (estimated 20%-28%).[1] According to the 2011 Demographic and Health Survey, 74% of pregnant women in Zambézia attended at least one prenatal visit.[2] In our 2014 unpublished Presidents Emergency Plan for AIDS Relief (PEPFAR) program data, 81% of pregnant woman who came to the antenatal clinic (ANC) were tested for HIV, but only 80% of them initiated antiretroviral therapy (ART). Half of HIV+ pregnant women abandoned care within six months of ART enrollment. Fewer than 40% returned with their infants for Early Infant Diagnosis (EID) services. Among returnees, only 70% of infants received a PCR test to determine HIV status and only 30% of HIV-infected infants were enrolled on ART (unpublished data, FGH-Zambézia). Thus, only 2% of women received all steps of the cascade necessary for PMTCT, probably the lowest program coverage rate in all of sub-Saharan Africa.

In Mozambique, all HIV-infected pregnant women are now eligible for life-long antiretroviral therapy (ART), regardless of CD4+ cell count (Option B+).[3-5] However, retention in care among women enrolled through Option B+ programs remains sub-optimal in sub-Saharan Africa (SSA) [6-8] primarily due to the need for male partner approval to access health services.[9] Poor medication adherence in Option B+ programs increases risk of mother-to-child transmission and ART resistance.[10, 11] In 2012, there were 94,000 HIV-positive pregnant women in Mozambique.[12] PEPFAR implementer, Friends in Global Health data indicated 8.0% of all pregnant women were HIV-positive; 60% had HIV-infected partners in 2014.[9] Eighty percent of HIV-infected pregnant women and <10% of HIV-infected partners identified during antenatal care (ANC) enrolled on ART. Retention was abysmal: 50% of women and 88%

of men abandoned care within six months (FGH M&E data). At one year, 8% of exposed infants in Mozambique were HIV infected vs. only 1.8% in neighboring South Africa.[13, 14]

Role of Male Partners in Retention and Adherence to HIV Health Services

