Question 4: Is the intervention cost-effective? Would the Ministry of Health be willing to scale it up based on our costing data?

7. Study Population

a. Population:

Couples consisting of two adults 18 years or older (one HIV-infected pregnant woman and her HIV-infected male partner) presenting for ANC services together at one of 24 clinical sites in Zambézia province.

b. Inclusion Criteria:

Couples, one HIV+ pregnant woman and her infected male partner, will be eligible to participate if the woman's due date is >2 weeks from enrollment. Both persons must also be 18 years or older, able to give consent, willing to consent to an infant record search, and must agree to enroll in ART together.

c. Exclusion Criteria:

Couples will not be eligible to participate in the study if the woman is not pregnant, if both persons are not HIV+, if either person is younger than 18 years, if one member of the couple is unwilling to enroll in ART or consent to the infant record search, or if one member of the couple is unable to give consent due to mental limitations.

d. Calculations of Sample Size:

Objectives 1 & 3: With 24 clusters and 45 couples per cluster, we have over 80% power to detect a 30% increase in the proportion of pregnant women who initiate ART from 55% to 71.5% with $\alpha = 0.05$. Our power calculations count adults and babies who dropout during the EMTCT cascade (e.g. do not initiate ART) as failures for downstream aims (e.g. retention on ART or viral suppression). For example, SOC ART retention was calculated as the proportion of women who initiated ART multiplied by the proportion of women retained in care ($0.55 \times 0.56 = 0.31$). In our sample size calculation, we power for a 20% increase in adult ART retention (above and beyond the 30% increase in adult ART initiation, for an improvement in retention from 31% to 48%), 90% vs. 80% viral suppression among women or men, 20% increase in EID testing, and 40% reduction in infant HIV positivity. Women, men and infants will be evaluated as separate study populations.

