Friends in Global Health supports HIV care and treatment services to 88 clinical sites in the province. Our trial will involve 24 of these clinics. These sites range from small district-level hospitals to rural health posts. All provide Option B+ services free of charge to HIV-infected pregnant women and their partners. In 2015, FGH clinics tested 95% (114,857) of the pregnant women presenting for ANC for HIV and provided Option B+ ART services to 87% (8,137 newly diagnosed women); 3,000 HIV-infected men were identified through ANC-based couples counseling.

Table 2: Study Sites by intervention Status

	Intervention sites		Control sites	
	Health Facility	District	Health Facility	District
1	Muiane CS III	Gilé	Mocubela CS III	Mocubela
2	Mixixine CS III	Namacurra	Inhassunge CS I	Inhassunge
3	Palane-Mucula CS II	Inhassunge	Mugubia CS	Namacurra
4	Gurai PSA	Mocubela	Bingagira PS	Inhassunge
5	Muebele PS	Namacurra	Gonhane CS III	Inhassunge
6	Maganja da Costa CS III	Maganja dC	Gilé CS II	Gilé
7	Naburi CS III	Pebane	Tapata CS III	Mocubela
8	Nante CS III	Maganja dC	Malei PS	Namacurra
9	Tomeia PSA	Pebane	Pebane CS II	Pebane
10	7 de Abril CS III	Pebane	Magiga PSA	Pebane
11	Pele-Pele CS	Pebane	Alto Maganha CS	Pebane
12	Madal CS	Quelimane	M'Baua CS III	Namacurra

10. Data Management and Analysis

Data Management and Security

The data collected will be kept in a database housed in Mozambique. Data will be stored in a restricted access folder that sits on the FGH server. In addition, data will be password-protected to limit access to staff involved in the study and to ensure confidentiality. Data will be encrypted, backed up on FGH servers, and uploaded to the Vanderbilt servers as needed for PI access. FGH servers have daily backups scheduled; therefore, all data will be backed up on a day-to-day basis.

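### The 55% standard-of-care ART initiation rate behind the power statement has no source and is not reconciled with the protocol's own 80% and 87% programme rates

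*Combined protocol and SAP*

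**What the plan says.** Section 7d (Calculations of Sample Size, Objectives 1 & 3) states that "we have over 80% power to detect a 30% increase in the proportion of pregnant women who initiate ART from 55% to 71.5" per cent, at alpha 0.05 with 24 clusters of 45 couples. It carries the same 55% into the retention contrast: "SOC ART retention was calculated as the proportion of women who initiated ART multiplied by the proportion of women retained in care", that is 0.55 × 0.56 = 0.31. A further 20% gain in retention on top of the initiation gain is then assumed, "for an improvement in retention from 31% to 48" per cent. No source is given for 55% or for 0.56, and no intracluster correlation (ICC) is stated.

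Elsewhere the protocol reports higher initiation:

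- Background, 2014 programme data: of HIV-positive women in antenatal care, "only 80% of them initiated antiretroviral therapy (ART").
- Background, next paragraph: "Eighty percent of HIV-infected pregnant women" identified in antenatal care enrolled on ART.
- Section 9 (Locations of Study), 2015: the supported clinics "provided Option B+ ART services to 87% (8,137 newly diagnosed women"). The 24 trial sites are drawn from this network: "Friends in Global Health supports HIV care and treatment services to 88 clinical sites in the province".

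Section 7b adds that both members of a couple "must agree to enroll in ART together".

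**The concern.** The planned initiation effect is relative (0.55 × 1.30 = 0.715), so its feasibility depends on the baseline. The only initiation rates that the protocol reports for pregnant women are 25 and 32 points above the one it plans with. Nothing explains why women in couples who have agreed to ART would start less often than programme clients in general.

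The figure also feeds a second contrast. Retention is a named Objective 1 outcome, and its 31% is the product of 55% and 0.56. If 55% is wrong for the trial population, neither contrast describes what the trial can expect to see, and a reader cannot tell whether the stated power applies.

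**Working it through.** **Inputs from the protocol.** Section 7d: 55%, 71.5%, 0.56, 31%, 48%, 45 couples per cluster, 24 clusters. Section 6: 12 clinics per arm, matched pairs. Background: 80% initiation; half of women abandoning care within six months of ART enrolment. Section 9: 87%. Section 7e: enrolment stops at 40 couples per site.

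**Step 1. Reproduce the plan's rates.** 0.55 × 1.30 = 0.715. 0.55 × 0.56 = 0.308 (stated 31%). 0.715 × 0.56 × 1.20 = 0.480 (stated 48%). The arithmetic is right; the question is the input.

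**Step 2. Can 55% be derived from the background figures?** Multiplying cascade steps does not give it: 0.81 × 0.80 = 64.8%, and 0.74 × 0.81 × 0.80 = 48.0%.

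**Step 3. Apply the 30% relative increase to the programme rates.** 0.80 × 1.30 = 104%; 0.87 × 1.30 = 113%. Neither is possible. The largest baseline that allows it is 1/1.30 = 76.9%. The same 16.5-point absolute gain is possible from 80% (96.5%) but not from 87% (103.5%).

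**Step 4. Standard-of-care retention on the plan's construction.** With 0.56: 0.80 × 0.56 = 44.8% and 0.87 × 0.56 = 48.7%. With the background's 50%: 0.80 × 0.50 = 40.0% and 0.87 × 0.50 = 43.5%. All exceed 31%.

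**Step 5. Illustrative power.** My assumptions, not the protocol's:

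- two-sided 0.05, 45 per clinic, 22 degrees of freedom;
- ICC 0.02 to 0.05, no precision gain from matching;
- the planned odds ratio held constant: (0.715/0.285)/(0.55/0.45) = 2.05, so 80% becomes 89.1% and 87% becomes 93.2%;
- intervention retention = initiation × 0.56 × 1.20 = initiation × 0.672.

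Power comes from the noncentral t with noncentrality |p2 − p1|/SE, where SE² = [p1(1 − p1) + p2(1 − p2)] × [1 + (m − 1) × ICC]/(12m) and m is the number per clinic. The design effect for m = 45 is 1 + 44 × 0.02 = 1.88 or 1 + 44 × 0.05 = 3.20.

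Worked example, 80% to 89.1% at ICC 0.02: SE² = 0.2568 × 1.88/540, SE = 0.0299, noncentrality = 0.0914/0.0299 = 3.06, power 83%.

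| Initiation baseline | Initiation contrast | Power, ICC 0.02 / 0.05 | Retention contrast (with 0.56) | Power, ICC 0.02 / 0.05 |
|---|---|---|---|---|
| 55% (plan) | 55 to 71.5% | 98 / 86% | 31 to 48% | 98 / 88% |
| 80% | 80 to 89.1% | 83 / 61% | 44.8 to 59.9% | 94 / 77% |
| 87% | 87 to 93.2% | 67 / 45% | 48.7 to 62.6% | 90 / 70% |

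The largest ICC that keeps 80% power for initiation is 0.063 as planned, 0.024 from 80% and 0.009 from 87%.

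**Step 6. Sensitivity.**

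- With 40 per clinic and 11 degrees of freedom (12 pairs), initiation power in the same order is 96–81%, 77–56% and 60–41%; retention power is 97–84%, 90–71% and 85–64%.
- A 16.5-point gain from 80% (to 96.5%) keeps about 99% power at ICC 0.05, even with 40 per clinic and 11 degrees of freedom.

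**The case against.** **The populations differ.** The programme rates cover HIV-positive antenatal clients across the supported clinics; the trial enrols seroconcordant couples at 24 of them. Agreement to enrol in ART is an intention given at consent, not initiation. Section 9 reports provision of services, which may not match the trial's definition of initiation. The two 80% statements may be one figure given twice. All of this stands, and any baseline up to 76.9% leaves the 30% increase possible. But the protocol does not offer this explanation, and it cites nothing for 55% in couples.

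**The retention revision keeps another unsourced input.** It does: 0.56 has no source either, so the revised figure is better given as 40.0–48.7% across both choices. The 31% to 48% contrast also depends on the assumed 20% gain, not on 55% alone. A reader might infer that, at 87%, control retention (48.7%) already exceeds the intervention target of 48%. That sets a revised control rate against an unrevised target: on the same construction the target moves to 62.6%, and with 50% retention the control rate is only 43.5%.

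**The power loss comes from the reviewer's choices.** Largely so. The odds ratio and the ICC range are assumptions, and a 16.5-point gain from 80% loses nothing of consequence. The 11-degree scenario charges the cost of matching without crediting any gain in precision. Objective 1 in section 5 also names retention, viral suppression and early infant diagnosis rather than initiation, and retention power stays at 85% or more at ICC 0.02 in every scenario above. These points limit the claim about power; they do not remove the unexplained baseline.

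**Conclusion.** The planning input is wrong as written and should be corrected. The power statement rests on an unsourced 55% that the protocol's own 80% and 87% contradict without explanation. If the programme rates hold for trial women, the stated relative effect is arithmetically impossible and standard-of-care retention is 40.0–48.7%, not 31%.

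A reader might go further and conclude that the trial is underpowered. The documents do not support that. The true baseline among enrolled couples is unknown, the ICC is not stated, and the effect that would replace the 30% is open. Under the assumptions in the working, power above 80% survives in part of the range and fails in part: for initiation 83–61% from 80% and 67–45% from 87%; for retention 94–77% and 90–70%. What is established is an unreconciled baseline that leaves the stated power unverifiable.

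**What to change.** In section 7d, do one of two things. Either cite the source that justifies 55% and 0.56 for enrolled seroconcordant couples, or replace both with the best available standard-of-care rates. The site-level ART uptake and retention data that section 6 uses for matching are an obvious candidate, with a note on how clinic clients differ from enrolled couples.

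Then choose an initiation effect that is attainable from that baseline, recompute the standard-of-care and intervention retention rates from it, and restate power or the detectable difference. State the ICC, and use one cluster size after reconciling 45 per cluster (section 7d) with 40 per site (section 7e).

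The cost is rewriting one paragraph with data the team already needs. The downside is that the stated power may become less favourable. The change does not itself ask for more participants.

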This study is important because it targets the health and well-being of the mother-infant-male partner triad,^[50] the essential family group that has eluded effective engagement strategies in HIV care. It builds on our research team's extensive experience in: (1) HIV care and treatment; (2) male partner engagement; (3) and cost-effectiveness analysis. Our results will improve outcomes by effectively engaging couples in HIV care and treatment during pregnancy and beyond. Without effective innovation in culturally appropriate adherence support to all stages of the care continuum, EMTCT efforts will fail in rural Africa.

6. Design and Study Questions

We propose to conduct a matched-pair cluster Randomized Controlled Trial to evaluate the effects of our intervention. To our knowledge, this is the first ANC-based couples study that will assess definitive treatment outcomes within a randomized controlled trial (RCT), and analyze the cost-effectiveness of the intervention. Twenty-four primary and secondary level health care facilities in Zambézia Province will be matched and then randomized to the control (standard-of-care [SOC]) or intervention (HoPS+) arms (12 sites per arm). We opted for a study design in which the unit of randomization is the EMTCT clinic (not the individual) because it would be extremely difficult to implement the intervention to only a subset of clients within each facility. We will match clinics on ART uptake rates, retention in care among patients on treatment, patient volume, HIV prevalence in ANC, and level of facility (secondary or primary)^[51] using reweighted Mahalanobis distances^[52] and then randomize clinics in each matched pair to intervention and SOC arms – 12 clinics per arm, 24 total. Intervention and control sites will be >100 km of each other to prevent contamination.

There are four specific study questions:

Question 1: Is our intervention idea (partners-based ART services for expectant and post-partum couples) acceptable to expectant couples?

Question 2: Does our intervention positively impact partner support for ART medication adherence and retention in care? Does it increase empathy among partners enrolled? Does it increase knowledge about HIV? Does it reduce HIV stigma among couples enrolled into the intervention?

Question 3: Does our intervention improve the proportion of exposed infants who are tested for HIV (early infant diagnosis)? Does it decrease the number of infants who are HIV-positive at 12 months?

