Objective 2: Aim 2 analyses will utilize a subset of the 1,080 enrolled couples (2,160 individuals) who are alive and can be contacted to provide data by 6 months after enrollment, regardless of whether or not they are retained in care. Because the psycho-social data collected by 6 months may be influenced by whether or not participants were retained through 6 months, our analyses will initially only consider retention outcomes after 6 months to maintain the temporal order needed to infer any mediation effects.

e. Sampling

Participants: HIV infected couples will be enrolled for 6 months at each study site. Patients will be enrolled on a first come, first enrolled basis until 40 couples have been enrolled.

[figure not shown]
f. Patient participant retention and withdrawal:

As per standard clinic procedure, couples on the control arm will receive separate clinical services at the ANC building and the adult HIV clinic, respectively. Peer educators will track all clients who miss appointments at control and intervention sites. The Home Based Care workers will document clients as terminating care if they: (1) discontinued services due to death; (2) transferred their care to another clinic that is not in the study; (3) are lost to follow-up (defined as being >90 days late for a clinic appointment plus 3 failed attempts at tracking the client); or (4) discontinue for any other reason, including patient choice. Clients will not receive any remuneration for participating in the study, per Mozambican National Medical Ethics Committee, but interview participants will be provided a small snack. Clients will be allowed to discontinue participation and may decide that their medical data cannot be used in the analysis at any time during the study.

8. Methods

a. Study Procedures

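### Section 7d says the trial is powered for a 40% cut in infant HIV without the inputs to support it, and the denominator for viral suppression and the handling of untested infants are also left open

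*Combined protocol and SAP*

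**What the plan says.** Section 7d (Calculations of Sample Size) plans 24 clinics with 45 couples each. It claims over 80% power at alpha 0.05 for a 30% "increase in the proportion of pregnant women who initiate ART from 55% to 71.5"%. It adds a further 20% gain in retention, "for an improvement in retention from 31% to 48"%, and then lists "90% vs. 80% viral suppression among women or men, 20% increase in EID testing, and 40% reduction in infant HIV positivity" as effects that the calculation also covers. The power calculations "count adults and babies who dropout during the EMTCT cascade (e.g. do not initiate ART) as failures for downstream aims", and viral suppression is one of the downstream aims named. No ICC appears anywhere in the documents, although clinics are randomised and the Section 10 model has a clinic random effect.

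Section 6, Question 3 asks "Does it decrease the number of infants who are HIV-positive at 12 months". The background section states "At one year, 8% of exposed infants in Mozambique were HIV infected"; Section 7d does not refer to that figure. The background also reports 2014 programme data in which fewer than 40% of HIV-positive pregnant women came back with their infants for early infant diagnosis (EID). It continues: "Among returnees, only 70% of infants received a PCR test to determine HIV status".

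Section 7e (Sampling) says "Patients will be enrolled on a first come, first enrolled basis until 40 couples have been enrolled", which is 40 per site rather than 45.

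Section 10 (Data Analysis, Objective 1) commits all analyses to intention to treat. For infants without an EID result it plans a sensitivity analysis by multiple imputation. It assigns infection probabilities where the mother never started ART or had left care by delivery.

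**The concern.** Three gaps meet in one paragraph of the sample-size section.

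- **Infant HIV.** A reader takes from 7d that the trial can detect a 40% cut, but the inputs needed to check this are absent. If real power is well below 80%, a null infant result could be read as evidence of no effect.
- **Viral suppression.** If drop-outs count as failures, suppression cannot exceed initiation, yet both suppression figures do. A reader cannot tell what share of enrolled adults the target means, or which comparison was powered.
- **Untested infants.** Testing is itself something the intervention aims to change, so missing infant results may differ by arm. The plan gives a probability for only some untested infants, and only in a sensitivity analysis. How the main analysis treats them is not stated.

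**Working it through.** **Method.** Two-sided 0.05, normal approximation with unpooled variance. For each arm, variance = p(1−p)/n × [1+(m−1)×ICC], where m is the mean number analysed per clinic. Power = Φ(difference/SE − 1.96). The ICCs and the two-sided test are assumptions, because 7d gives neither. With only 24 clinics, a t-based test would give somewhat less power.

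**The plan's own figure.** Initiation 55% vs 71.5%, n = 12 × 45 = 540 per arm. SE at ICC 0 = √[(0.55×0.45 + 0.715×0.285)/540] = 0.0289; 0.165/0.0289 = 5.71; power above 99.9%. At ICC 0.05 the design effect is 3.20, SE 0.0517, ratio 3.19, power 89%. At ICC 0.10 the design effect is 5.40, SE 0.0672, ratio 2.46, power 69%. The stated figure of over 80% is attainable up to an ICC of about 0.07. Without the ICC it cannot be reproduced.

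**Infant HIV, one scenario.** SOC 8% (assumed), intervention 0.6 × 8% = 4.8%, every infant evaluable. SE at ICC 0 = √[(0.08×0.92 + 0.048×0.952)/540] = 0.01486; 0.032/0.01486 = 2.15; power 57.7%.

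| ICC | Design effect (m=45) | Power, 45 per site | Power, 40 per site (480 per arm) | SOC rate needed for 80% (45 per site) |
|---|---|---|---|---|
| 0 | 1.00 | 58% | 53% | 12.9% |
| 0.01 | 1.44 | 43% | 41% | 17.8% |
| 0.02 | 1.88 | 35% | 33% | 22.2% |
| 0.05 | 3.20 | 22% | 22% | 33.3% |

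A one-sided test gives 69% at ICC 0. The expected 95% interval for the 3.2-point difference is 3.2 ± 1.96 × SE: 0.3 to 6.1 points at ICC 0 and −0.3 to 6.7 at ICC 0.01.

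**Viral suppression.** With drop-outs as failures, the ceiling over all enrolled is initiation (55% and 71.5%), or retention (31% and 48%) if leaving care also counts. So 80% and 90% must be conditional on an earlier step. Two steps and two ways of comparing give:

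| Comparison | Rates | n per arm | Power, ICC 0 | Power, ICC 0.05 |
|---|---|---|---|---|
| All enrolled, step = initiators | 0.55×0.80 = 44.0% vs 0.715×0.90 = 64.4% | 540 vs 540 | >99% | 97% |
| All enrolled, step = retained | 0.31×0.80 = 24.8% vs 0.48×0.90 = 43.2% | 540 vs 540 | >99% | 95% |
| Initiators only | 80% vs 90% | 297 vs 386 | 95% | 66% |
| Retained only | 80% vs 90% | 167 vs 259 | 79% | 55% |

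The last row in full: n = 0.31×540 = 167.4 and 0.48×540 = 259.2. SE at ICC 0 = √(0.16/167.4 + 0.09/259.2) = 0.0361; ratio 2.77. At ICC 0.05, m = 13.95 and 21.6 give design effects of 1.65 and 2.03, SE 0.0477 and ratio 2.09.

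**Untested infants.** In the 2014 programme data, under 0.40 × 0.70 = 28% of infants had a result. Section 10 ties its infection probabilities to the mother's ART start and her retention at delivery. An untested infant whose mother started ART and was still in care at delivery falls outside both conditions.

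**The case against.** The strongest reply is that 8% is a national background figure that 7d never adopts. The rate in the trial could be higher: Zambézia's programme coverage is described as very low, and Section 8b expects more transmission among those lost to care. If 8% applies only to tested infants, 28% are tested and the rest are infected at an assumed 15%, the baseline is 0.28×8% + 0.72×15% = 13.0%. Power is then about 80% without clustering and 65% at ICC 0.01. It could also be lower, since enrolled couples must agree to start ART together. This stands: 58% is a scenario, and a reader should not infer that the trial is shown to be underpowered for infant HIV.

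A second reply is that lost babies count as failures. If that means HIV positive, SOC positivity at 28% tested is 1 − 0.28×0.92 = 74%, and a 40% cut to 45% would be amply powered. That would be a different endpoint, driven mainly by testing, and 7d does not say it is the one meant.

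On suppression, the plan builds retention as a product of step rates (0.55 × 0.56), and 80% and 90% fit naturally as the next step. That is fair: a reader might infer an arithmetical error, but the documents show only an unnamed denominator. Nor should one infer that the choice is harmless for power; the table shows otherwise.

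On imputation, Section 10 does address missing EID results in general, so it would be wrong to say untested infants are ignored. The gap is the missing probability for one group and the unstated main analysis. The 28% figure comes from 2014 routine care, and missed visits are tracked in both arms, so the trial may do better.

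Finally, infant HIV is posed in Question 3 and is not among the outcomes named in Objective 1. That limits the consequence, but 7d still lists it as powered.

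**Conclusion.** The concern holds in this form. It is certain, without any assumption, that the infant HIV power claim lacks a baseline, ICC, sidedness, power level and rule for lost or untested infants, and cannot be checked. With 8% assumed as the SOC rate and all infants evaluable, power is about 58% at best and 22% to 43% at ICCs of 0.05 to 0.01. An SOC rate near 13% would reach 80% only with no clustering. The documents do not establish which baseline applies.

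It is equally certain that 80% and 90% suppression cannot be shares of all enrolled under 7d's own rule. Power is at least 95% at ICC 0.05 over all enrolled, but 66% among initiators and 55% among the retained, so the denominator has to be named. The last two comparisons also condition on steps that the intervention is meant to change, which sits poorly with intention to treat.

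Untested infants of mothers retained at delivery have no assigned infection probability in the sensitivity analysis, and the primary handling of all untested infants is unstated. This should be fixed before analysis. Confidence in the infant power figures is medium, because the baseline and the ICCs are assumed.

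**What to change.** 1. **Section 7d, infant HIV.** State the SOC rate with its source, the ICC, the sidedness, and how a lost or untested infant counts. Replace the unqualified claim with the power that these give. If it is below 80%, say so, and report infant HIV as an estimate with its interval.
2. **Section 7d and Section 10, suppression.** Restate the target as a share of all enrolled with drop-outs as failures, in line with 7d's rule and the intention-to-treat commitment. Give the men's inputs separately, because the initiation and retention inputs shown (0.55 and 0.56) are for women. Name the same denominator in Section 10.
3. **Section 10, untested infants.** State the primary handling of infants without a result. Extend the planned multiple imputation to every such infant, including those of retained mothers, and vary the assumed infection probabilities.

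The cost is sample-size and analysis-plan wording and a little extra analysis, with no change to enrolment or data collection. The stated infant power may become less favourable, and the imputation will still rest on assumed probabilities, which is why they should be varied.
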